2 INTRODUCTION

2.1 BACKGROUND OF DISEASE

Isolated cervical dystonia (CD) is a chronic neurologic disorder characterized by involuntary patterned contractions of cervical musculature resulting in abnormal movements or postural changes of the head, neck, and shoulders. The pattern of neck muscle involvement in patients with CD is variable, leading to clinically heterogeneous directional presentations, such as rotational torticollis, laterocollis, retrocollis, or anterocollis (*Stacy 2008*). Additional signs and symptoms may also include head oscillation due to dystonic tremor produced by uneven contractions of the cervical muscles, neck/shoulder pain, shoulder elevation, and arm tremor (*Phukan et al. 2011, Stacy 2008, and Schiebler et al. 2011*). Non-motor symptoms of CD may negatively impact mood and emotions, resulting in depression, social withdrawal, impaired sleep, poor health outcomes, and diminished quality of life (QOL) (*Ben-Shlomo et al. 2002; Jahanshahi, 1991; Lim 2007; Gundel et al. 2001; Zetterberg et al. 2012; and Kuyper et al. 2011*).

[figure not shown]
There is a lack of clinical diagnostic guidelines to allow easy differentiation of CD from other disorders of the neck that may simulate dystonia, and because of the wide variability in CD clinical features among individual patients, the diagnosis of CD can be open to misinterpretation and misdiagnosis. Hence, the data are limited regarding the incidence and prevalence of CD. Despite the varying prevalence estimates in the literature, an approximate 2:1 female to male ratio was consistent among many studies (*Defazio et al. 2013*).

[figure not shown]
[REDACTED]

[figure not shown]
[REDACTED]

[figure not shown]
[REDACTED]

[figure not shown]
[REDACTED]

[figure not shown]

[figure not shown]

[figure not shown]

[figure not shown]

3 OBJECTIVES AND ENDPOINTS

OBJECTIVES	ENDPOINTS	JUSTIFICATION FOR ENDPOINTS
Primary:		

• To evaluate the long-term safety of multiple continuous treatments of DAXI for injection• To assess immunogenicity of BoNTA and RTP004 after multiple treatments of DAXI for injection	
• The dose- and cycle-specific incidence of drug-related AEs• The dose- and cycle-specific incidence of study drug discontinuation due to drug-related AEs• The dose and cycle-specific incidence of treatment-emergent immunogenicity	Clinically relevant outcome measures for this indication

4 STUDY DESIGN

4.1 OVERALL DESIGN

This is a Phase 3, open-label, multi-center trial to evaluate the long-term safety, efficacy, and immunogenicity of up to four continuous treatments of multi-dose DAXI for injection (125 U, 200 U, 250 U, and 300 U) in adults with isolated CD.

Approximately 350 adult subjects will be recruited from study centers in the US, Canada, and Europe who were enrolled in Study Protocol 1720302. These subjects from 1720302 include:

- Those with no reduction or have an increase from baseline in the average TWSTRS-total score at Weeks 4 and 6 (i.e., no improvement or worsened disease status), and the investigator agreed that there was a need for retreatment based on the subject's symptoms and neurologic exam findings
- Those who benefited from study treatment and completed follow up study visits up to the time point of when their TWSTRS-total score reached/exceeded their target TWSTRS score
- Those who benefited from study treatment but subsequently experienced significant recurrence of CD symptoms (e.g. pain) during the study before their TWSTRS-total score reached their target TWSTRS score and requested retreatment, which the investigator determined was warranted based on the subject's symptoms and neurologic exam findings
- Those who completed study visits up to Week 36 and their TWSTRS-total score never reached their target TWSTRS score and they never requested another treatment. The investigator determined that these subjects can be followed in the OLS until their TWSTRS-total score is the same or higher than their target TWSTRS score or until they request retreatment, which the investigator determined is clinically indicated

All subjects will have up to 7 days from their End-of-Study (EOS) Visit in Study Protocol 1720302 to decide if they want to enroll in the OLS. After the 7-day decision-making period, any subjects who have not made an enrollment decision will be considered "not interested in the OLS."

After a subject has decided to enroll in the OLS, s/he will have up to 21 days to complete the screening procedures and enroll in the OLS. After 21 days, subjects who have NOT completed the screening procedures will be considered a screen failure. To be reconsidered for enrollment to the OLS, the subject

will be required to repeat all screening procedures to reconfirm eligibility for enrollment in the OLS. These criteria also apply to subjects who missed the 7-day decision-making window to enroll in the OLS.

A written informed consent must be obtained from all subjects participating in the OLS before any trial-related procedures (including any screening procedures) are performed.

Eligible subjects who completed participation in Study Protocol 1720302 may be eligible for the first treatment (Baseline Treatment in Treatment Cycle 1 of OLS) during their EOS Visit window, but treatment may not be administered on the same day as the EOS Visit due to unavailability of screening safety laboratory results. In this case, the EOS Visit procedures and laboratory results from Study Protocol 1720302 will serve as the baseline data for this trial.

This study will also recruit new BoNT treatment-naïve or -experienced adult subjects, who were not enrolled in Study Protocol 1720302.

[REDACTED]

[REDACTED]

[REDACTED]

- [REDACTED]

- [REDACTED]

[REDACTED]

- [REDACTED]

- [REDACTED]

[REDACTED]

[REDACTED]

[REDACTED]

[REDACTED]

[figure not shown]
[REDACTED]

[REDACTED]

[REDACTED]

[REDACTED]

[REDACTED]

4.3 STUDY VISITS AND TELEPHONE CALLS

[figure not shown]
Figure 3 summarizes the schedule of telephone calls and assessments by treatment cycle.

[figure not shown]
- Screening (Days -21 to -1)
- Baseline Treatment #1, Treatment #2, #3, #4
- Follow-up telephone call after each Treatment:
 - Week 2 after each treatment (study site staff will call the subject)
- Follow-up visits after each Treatment:
 - Weeks 4, 6, 12, and every 4 weeks thereafter until Week 52/End-of-Study Visit (See Figure 1 and Table 1)

[figure not shown]
Safety assessments include laboratory tests (hematology, PT, chemistry, and urinalysis), [REDACTED], [REDACTED], physical and neurological examinations, the C-SSRS, Dysphagia Severity Scale, vital signs, pulmonary function by spirometry, 12-lead ECGs, injection site evaluations, concomitant medications, AE monitoring at protocol-specified timepoints, [REDACTED]

Efficacy assessments, including the TWSTRS (total score and subscale scores), CDIP-58, CGIC, PGIC, TSQ, WPAI, and SF-36 Survey, will be performed at protocol-specified timepoints as outlined in the SOA (Table 1).

No interim analysis is planned for this study.

5 STUDY POPULATION

5.1 INCLUSION CRITERIA

All participants must meet the following inclusion criteria:

1. Adults, 18 to 80 years of age

[figure not shown]
2. Meets diagnostic criteria for isolated CD (idiopathic; dystonic symptoms localized to the head, neck, shoulder areas) with at least moderate severity at Baseline (Day 1), defined as a TWSTRS-total score of at least 20, with at least 15 on the TWSTRS-Severity subscale, at least 3 on the TWSTRS-Disability subscale, and at least 1 on the TWSTRS-Pain subscale (minimum TWSTRS subscale criteria applicable only to subjects not previously enrolled in Study Protocol 1720302)
3. Subjects who were previously enrolled in Study Protocol 1720302, who completed the study, including:
 - a) Those with no reduction or have an increase from baseline in the average TWSTRS-total score at Weeks 4 and 6 (i.e., no improvement or worsened disease status), and the investigator agreed that there was a need for retreatment based on the subject's symptoms and neurologic examination findings
 - b) Those who benefited from study treatment and complete follow-up study visits up to the time point of when their TWSTRS-total score reached/exceeded their target TWSTRS score
 - c) Those who benefit from study treatment but subsequently experienced significant recurrence of CD symptoms (e.g., pain) during the study before their TWSTRS-total score reached their target TWSTRS score and requested retreatment, which the investigator determined was warranted due based on the subject's symptoms and neurologic examination findings
 - d) Those who completed study visits up to Week 36 and their TWSTRS-total score never reached their target TWSTRS score and they never requested another treatment. The investigator determined that these subjects can be followed in the OLS until their TWSTRS-total score is the same or higher than their target TWSTRS score or until they request retreatment, which the investigator determined is clinically indicated
4. De novo subjects (not previously enrolled in Study Protocol 1720302):
 - a) Naïve to BoNT treatment
 - b) BoNT treatment-experienced; if previously treated with BoNTA, the subject must have demonstrated a clinically meaningful response to the last BoNTA treatment based on the clinical judgment of the investigator
5. Written informed consent including authorization to release health information

[figure not shown]

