7.2 SUBJECT DISCONTINUATION/WITHDRAWAL FROM THE STUDY

Subjects are free to withdraw from participation in the study at any time with notification.

An investigator may discontinue or withdraw a participant from the study for the following reasons:

- Pregnancy
- Significant study intervention non-compliance (e.g., failure to follow study procedures or to keep follow-up appointments)
- If any clinical AE, laboratory abnormality, or other medical condition or situation occurs such that continued participation in the study would not be in the best interest of the subject
- The subject experiences no reduction or have an increase in the average TWSTRS-total score at Weeks 4 and 6 post-injection relative to the pre-injection TWSTRS-Total score at the beginning of the treatment cycle (i.e., **lack of efficacy**: no improvement or worsened disease status)
- If the investigator determines that another BoNT treatment is needed to control the CD symptoms and less than 12 weeks have elapsed since the last study treatment administration
- If the subject meets an exclusion criterion (either newly developed or not previously recognized) that precludes further study participation

If the subject withdraws consent and discontinues from the study, the investigator will record the reason for consent withdrawal, if one is provided by the subject, in the subject's study records and on the eCRF. If a subject withdraws consent because of an AE, that AE should be indicated as the reason for withdrawal. In the event of early discontinuation, the subject should be asked to return to the study center to complete the assessments specified in the EOS Visit.

If at any time during the study, the investigator determines that it is not in the best interest of the subject to continue, the subject will be discontinued from participation. The investigator can discontinue a subject at any time if medically necessary. Appropriate documentation in the subject's study record and eCRF

regarding the reason for discontinuation must be completed. Prior to discontinuing a subject from study participation, the investigator will discuss his/her intentions with the medical monitor or designee.

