8.1.2.4 END-OF-STUDY VISIT

The EOS Visit for each subject in the OLS may occur when the subject:

- Prematurely withdraws from the study for specific reasons (e.g., AEs, pregnancy, or withdraws consent)
- Has no improvement or worsened disease status (i.e., lack of efficacy) after a treatment (consistent with no change or increase from baseline in the average of the TWSTRS-total score at Weeks 4 and 6 post-treatment)
- Requires another treatment less than 12 weeks from the last injection
- Reaches Week 52

Refer to the SOA (Table 1) for EOS activities.

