9.6 PLANNED ANALYSES

All efficacy endpoints, including responder rates, will be summarized with descriptive statistics by dose and/or treatment cycle, unless otherwise specified.

Discontinuation rate will be summarized by dose and cycle as well as overall. Additionally, the number of weeks on study will be summarized with descriptive statistics.

Duration of effect after each treatment, defined as time (number of weeks) from treatment until loss of 80% of the peak treatment effect (i.e., the average of the change from baseline in the TWSTRS-total score at Weeks 4 and 6)

[figure not shown]
- If a subject has no reduction in the TWSTRS-total score at Week 4 and Week 6, his/her duration of effect will be set to 0. If a subject discontinues or withdraws from the study prior or at Week 6, his/her duration of effect will be set to 0.
- If a subject discontinues or withdraws from the study prior to reaching his/her target TWSTRS score at any visit after Week 6, his/her duration of effect will be censored at the last visit. If a subject rolled over from Study Protocol 1720302 at Week 36 prior to reaching his/her target TWSTRS score, his/her duration will be calculated from the injection date in Study Protocol 1720302 to the time his/her TWSTRS-total score reaches/exceeds the target TWSTRS score.

Kaplan-Meier survival curves will be plotted for each dose level for the time-to-event endpoints. Point estimate of median duration and 2-sided, 95% confidence intervals (CIs), will be generated using the log-rank test. A subject might be counted more than once or in multiple groups due to multiple injections cycle. Exploratory statistical comparisons between subgroups and duration of response evaluation may be performed.

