3.4. Brief Description

This is a Phase 3, open-label, multi-center trial to evaluate the long-term safety, efficacy, and immunogenicity of up to four continuous treatment cycles of DAXI for injection at doses of 125 U, 200 U, 250 U, and 300 U in adults with isolated CD at study centers across the United States, Canada, and Europe.

Approximately 350 adult subjects will be recruited from study centers who were previously enrolled in Protocol 1720302 entitled [A Phase 3, Randomized, Double-Blind, Placebo-Controlled, Parallel Group, Multi-Center Trial to Evaluate the Efficacy and Safety of a Single Treatment of DaxibotulinumtoxinA for Injection in Adults with Isolated Cervical Dystonia (ASPEN-1)]. These subjects will have 7 days from their End-of-Study (EOS) Visit in Protocol 1720302 to decide if they want to enroll in this study. After enrolling, subjects will have up to 21 days to complete screening procedures. After 21 days, subjects who have NOT completed the screening procedures will be considered a screen failure. To be reconsidered for enrollment to this study, the subject will be required to repeat all screening procedures to reconfirm eligibility for enrollment. These criteria also apply to subjects who missed the 7-day decision-making window to enroll in this study. This study will also recruit new botulinum neurotoxin (BoNT) treatment-naïve or -experienced adult subjects who were not enrolled in Protocol 1720302.

[REDACTED]

[REDACTED]

This document is confidential.

[REDACTED]

The primary endpoints are safety and immunogenicity. [REDACTED]

[REDACTED]

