7.5.2. Concomitant Medication

Medications that were taken on or after the first study medication dose date will be classified as concomitant. This classification includes medications that were started after the first study medication dose date or medications that began before and continued to be taken after the first study medication dose date.

[figure not shown]
This document is confidential.

8. Efficacy

[figure not shown]
All efficacy analyses will be performed for the safety population. Efficacy endpoints, including responder rates, will be summarized with descriptive statistics by dose and treatment cycle, unless otherwise specified.

[figure not shown]
This document is confidential.

[figure not shown]
This document is confidential.

[figure not shown]
This document is confidential.

[figure not shown]
This document is confidential.

This document is confidential.

This document is confidential.

This document is confidential.

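### Raw by-cycle TWSTRS means and responder rates compare different, response-selected subjects, so they can hide or mimic waning of effect

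*Protocol*

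**What the plan says.** **Leaving the study.** Protocol 7.2 lists among the reasons for which the investigator may withdraw a subject: "The subject experiences no reduction or have an increase in the average TWSTRS-total score at Weeks 4 and 6 post-injection relative to" the score before that cycle's injection. Section 8.1.2.4 lists as an occasion for the End-of-Study Visit: "Has no improvement or worsened disease status (i.e., lack of efficacy) after a treatment". Section 7.1 says further treatment depends on response to the previous one and may be withheld for lack of benefit. All three are permissive.

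**Timing.** Protocol 8.1.3 excludes retreatment at an unscheduled visit less than 12 weeks after the last injection or after Week 40 of the 52-week study.

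**Entry.** Criterion 3a admits subjects without improvement in Study 1720302: "Those with no reduction or have an increase from baseline in the average TWSTRS-total score at Weeks 4 and 6". SAP 3.4 gives that trial's title as a "Randomized, Double-Blind, Placebo-Controlled, Parallel Group, Multi-Center Trial to Evaluate the Efficacy and Safety of a Single Treatment of DaxibotulinumtoxinA" study, so 3a is not confined to subjects who had received DAXI. De novo subjects previously treated with BoNTA face the opposite filter: "the subject must have demonstrated a clinically meaningful response to the last BoNTA treatment" (criterion 4b).

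**Analysis.** Protocol 9.6: "All efficacy endpoints, including responder rates, will be summarized with descriptive statistics by dose and/or treatment cycle". SAP 8: "Efficacy endpoints, including responder rates, will be summarized with descriptive statistics by dose and treatment cycle", in the safety population. Protocol 9 planned multiple imputation of TWSTRS-total only up to discontinuation, and SAP 10 drops it. The visible sensitivity analyses (SAP 8.3) concern remote assessment and COVID-19. Discontinuation is tabulated by dose and cycle (Protocol 9.6), and reasons for it by cycle (SAP 7.1). Most of SAP 8 is redacted.

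**The concern.** The title and stated purpose of the trial include efficacy over up to four continuous treatments. A reader of a by-cycle table will ask whether the effect holds with repeated injections. That needs like-for-like groups across cycles, and here the group changes according to the outcome being tabulated.

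Two selections act. If subjects without improvement leave, later cycles are enriched for good responders. If subjects with long-lasting effect do not need retreatment in time, later cycles are enriched for short-lasting responders. The first can make a falling effect look stable. The second can make a stable effect look as if it wanes. Nothing in the visible analysis separates either from a real change in response.

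**Working it through.** The plan has no figure of its own to reproduce. The sample size (Protocol 9.1, SAP 3.6) is an exposure target of about 350 subjects treated once, at least 100 with 3 or 4 cycles and at least 50 of these at high dose. The visible text gives no SD, response rate or withdrawal rate, so every parameter below is an assumption.

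**1. Model.** Subject mean b ~ N(-10, 8). Week 4/6 average change in a cycle, from that cycle's pre-injection score, y = b + N(0, 6). Total SD = √(64 + 36) = 10; within-subject correlation = 64/100 = 0.64. Non-response is y ≥ 0, and a share q of non-responders leaves.

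**2. Cycle 2 by hand.**
- P(y ≥ 0) = P(Z ≥ 1) = 0.159.
- Cycle 2 mean of those who responded: -10 - 0.64 × 10 × φ(1)/Φ(1) = -10 - 6.4 × 0.2876 = -11.84. This is the raw mean when q = 1.
- Cycle 2 mean of those who did not respond: -10 + 6.4 × 0.2420/0.1587 = -0.24.
- With q = 0.5: [0.8413 × (-11.84) + 0.0793 × (-0.24)] / 0.9207 = -10.8.

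**3. Constant effect, four cycles (simulation).**

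| Non-responders leaving | Raw mean, cycles 1 to 4 | Improved ≥ 8 points, cycle 1 to 4 |
|---|---|---|
| All | -10.0, -11.8, -12.8, -13.4 | 58% to 73% |
| Half | -10.0, -10.8, -11.5, -12.1 | 58% to 67% |
| A quarter | -10.0, -10.4, -10.8, -11.1 | 58% to 63% |
| None | -10.0 throughout | 58% throughout |

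With all leaving, the spurious gain is 4.2 points if the true mean is -8 (-8.0 to -12.2) and 2.7 if it is -12 (-12.0 to -14.7). If responses were uncorrelated within subject there would be no drift.

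**4. True shrinkage of 10% per cycle.** Truth: -10.0, -9.0, -8.1, -7.3 (-10 × 0.9³ = -7.29), a loss of 2.7.

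| Non-responders leaving | Raw mean, cycles 1 to 4 | Apparent loss |
|---|---|---|
| All | -10.0, -10.7, -10.4, -9.9 | 0.1 |
| Half | -10.0, -9.8, -9.3, -8.8 | 1.2 |
| A quarter | -10.0, -9.4, -8.7, -8.1 | 1.9 |

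**5. Opposing selection.** Applying the 12-week and Week 40 limits to every retreatment, four injections need a mean interval of at most 40/3 = 13.3 weeks, and three at most 40/2 = 20 weeks. Assume interval = 12 weeks + 0.3 week per point of improvement, SD 3, never below 12. With constant effect and all non-responders leaving, the raw means are -10.0, -11.8, -11.9, -7.6, and only about 5% of subjects reach cycle 4. The spurious gain becomes a spurious loss. A weaker link leaves the drift upward.

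**6. Candidate remedies, all non-responders leaving.**
- Random-intercept model over all cycles (60 trials of 350): -9.97, -10.00, -10.04, -10.02 under constant effect. With the duration link, cycle 4 is -10.5. With 10% shrinkage: -10.0, -8.9, -7.7, -6.5 against a true -7.3, so waning is overstated (3.5 against 2.7).
- Subjects who received all four cycles, constant effect: -14.0, -14.0, -14.0, -13.4. Membership requires improvement in cycles 1 to 3 but not in cycle 4, so the last cycle shows a small artificial drop of about 0.6.
- Counting earlier lack-of-efficacy exits as failures: 58%, 55%, 53%, 51% under constant effect, but only 7% in cycle 4 with the duration link, because lasting responders disappear while failures accumulate.

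**The case against.** A reader might infer that by-cycle figures must rise by construction. The documents do not support that. Exit for lack of efficacy is discretionary in 7.1, 7.2 and 8.1.2.4. With half or a quarter of non-responders leaving, 10% waning is understated but still visible, and the timing limits can reverse the sign.

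A reader might also infer from criterion 3a that cycle 1 is loaded with known DAXI failures. That does not follow. The earlier trial was placebo-controlled, the share of 3a entrants is not given, criterion 4b selects the other way, and the model above contains no 3a subjects at all. The argument rests on who continues within the OLS.

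Three further objections have weight. The primary endpoints are safety and immunogenicity. The visible efficacy analysis is descriptive, with any comparisons exploratory. Attrition by cycle will be tabulated, which lets a reader see that the groups differ but does not correct a mean or a responder rate. Finally, redacted parts of SAP 8 may already contain a like-for-like comparison, so the point applies to the visible plan only.

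**Conclusion.** The point holds in a limited form. Continuation depends on the earlier response, and the visible by-cycle summaries do nothing about it, so they can hide or mimic waning. Exits for non-response push later cycles upward: by 1.1 to 3.4 points at cycle 4 under the assumed constant effect with a quarter to all of non-responders leaving. The retreatment limits can pull the other way, and the net direction cannot be settled from the documents. The sizes rest on the assumed mean, SDs, exit share and, for the reversal, an assumed link between size and duration of response. This is a recommended improvement to a secondary reading of the trial. It does not affect the primary endpoints.

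**What to change.** In SAP 8, unless redacted text already provides it, add beside the raw tables:

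1. Week 4/6 change by cycle from one mixed model using all cycles of all treated subjects, with cycle and dose as fixed effects and subject as random effect. State that it assumes missing at random, which discretionary exits and exits for early need of toxin may strain, and that it may overstate waning if effects shrink proportionally.
2. Each cycle's results within the sets of subjects who received at least 2, at least 3 and 4 cycles, with a note that the last cycle in each set can look slightly worse through selection alone.
3. Optionally, and labelled as a sensitivity analysis, a responder summary that counts earlier lack-of-efficacy exits as non-responders. It should show separately the subjects not retreated because their effect was lasting.
4. A sentence that raw by-cycle rates alone are not evidence of maintained effect.

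Showing cycle 1 with and without 3a entrants is a secondary extra. No clinical rule or data collection changes. The cost is one model, a few table panels and possibly less favourable later-cycle figures.
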